## 4. POPULATIONS FOR ANALYSIS

### 4.1 Intent-to-Treat (ITT) Population

The intent-to-treat population includes all patients that have been randomized to one of the three study arms. Patients will be analyzed in the group to which they were randomized, whether or

not they received their assigned treatment, any treatment whatsoever, or completed their treatment course and follow-up.

#### **4.2 Safety Population**

The safety population is defined as all ITT patients who received at least one dose of study medication. Patients who do not receive any study treatment (CPP-1X or sulindac or their combination) are excluded from this population. Patients will be analyzed in the treatment group according to which actual treatment was initially received.

#### **4.3 Per Protocol Population**

The per-protocol population is defined as the subset of the ITT population that fulfill all protocol eligibility, intervention, and outcome assessments.

#### **4.4 Other Populations**

Within the entire study patient population there will be subsets who did not receive the full course of per protocol treatment. The major indicators for premature withdrawal are delineated below. The patient diary and pill count will define the extent of treatment compliance during the study.

For exploratory and sensitivity analyses the following subsets will be included in secondary analyses:

- Patients withdrawn for personal reasons
- Treatment discontinued because of disease symptoms
- Treatment discontinued because of patient symptoms
- Compliance <80% treatments taken
- Treatment discontinued because of intercurrent medical or surgical illness.

### **5. DETERMINATION OF SAMPLE SIZE AND STATISTICAL METHODS**

#### **5.1 Determination of Sample Size**

The primary endpoint of this trial, time to meaningful clinical events in an orphan disease population, is novel and to date there are no published trials to draw upon that have incorporated the exact FAP-related endpoint of this trial. Available data from primary literature sources include clinical studies where polyps were counted over a fixed time period, in different FAP populations (see protocol for tabulated listing).

From these data a reasonable range of event frequencies was estimated to produce the sample size and power calculations incorporated into this trial. These time-to-event estimates were reviewed by key FAP opinion leaders prior to finalization of the study design. The following reflects the possible range of FAP events it was thought plausible to observe.

#### **5.2 Power Calculation Assumptions**

- 1) The level of statistical significance is set at 0.05, using a 2-sided stratified log-rank test for time-to-first FAP-related event in continuous time, for each of the two between-group comparisons (i.e. single agent sulindac vs. CPP-1X plus sulindac and single agent CPP-1X vs. CPP-1X plus sulindac). The only covariates in the log-rank test will be the treatment groups (see section 7.3 for details);
- 2) A doubling of the two-year event-free proportion from either of the single agent treatment arms to the combination treatment group;

- 3) Power of at least 85% to detect the above-mentioned treatment effect comparing either of the two single treatment arms to the combination arm;
- 4) The two single-agent treatment groups have approximately the same event rate.

The following calculations are based on our review of limited single-agent data for eflornithine and sulindac, where FAP clinical trial primary endpoints involved polyp counting. Extrapolating these data to two-year event-free proportions implies a single overall two-year event-free proportion of at least 60% to 70% for the combination treatment group and 30% in each single agent treatment group. This is described further in Table 3.2.

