We note that this approach is both a fixed-sequence and gatekeeping approach. It is fixed-sequence in that the comparison of combination with single-agent Sulindac takes place before the comparison of combination with single-agent Eflornithine and the first serves as a gatekeeper for the second (i.e., no declaration of significance in the second comparison will be made if the first comparison is not significant at the 0.05 level). Therefore, the type I error in the sequential testing is well controlled. In addition, because both tests must be significant for EMA approval, the type I error of the second test in the sequence is less than 0.05.

The analytic method for the primary analysis will be a time-to-event analysis using the stratified log-rank test. The stratified Cox proportional hazards regression models will be used for secondary assessments. Graphical analyses (log-minus-log plots) will be used to check the assumption of constant hazard ratios. For the primary analysis, two stratified log-rank tests will be performed with treatment coded as a binary value (i.e., 0 or 1). Time to event curves will be displayed using the method of Kaplan and Meier. Additional analyses involving the overall 3-treatment group comparison and use of additional study populations or the two pairwise treatment comparisons, will be performed as supplemental analyses.

If an FAP-related event occurs, that patient will be said to have an observed or uncensored event and will be considered a treatment failure. If a subject withdraws, that subject will be treated as a censored observation as of the last recorded clinic visit (endoscopic disease assessment).

If a subject has not progressed or is not known to have died at the date of analysis cut-off, time to first FAP-related event will be censored at the date of the last adequate endoscopy procedures before the cut-off date. Similarly, if a subject discontinues study participation due to toxicity and begins receiving other therapy, the time to FAP event will be censored at the date of the last adequate endoscopy procedure.

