For the anticipated range of hazard ratios, 25 to 49 events would be needed for each two-group comparison at the 2-sided 0.05 level to achieve 85% power. Assuming two-year event proportions of 70% in either of the two single-agent groups and 30% to 40% in the combination arm with 50 patients per arm, the expected number of patients with an FAP-related event in either of the two single-agent groups would be 35 and 15 - 20 in the combination arm. The study design expectation is to have 50 - 55 patients with a FAP-related event in each two arm comparison, achieving at least 85% power under the design alternative. The standard deviation around the expectation of 55 events is 4.74, so observing the required number of 49 events or more would be highly likely (the probability is about 91%). If the total number of events in either comparison were only 43, there will still be 80% power to declare a significant treatment difference under the design alternative of 0.4243.

As the two-year event proportion in the combination arm decreases from 40% with a corresponding decrease in the hazard ratio, the likelihood of observing the required number of events to maintain 85% power actually increases. For example, at the lower expectation of 50 events arising from an assumed two-year event proportion of 30% in the combination arm, the standard deviation of the total number of events in a two-arm comparison decreases to 4.58 and the probability that the observed number of events will exceed the 25 required to achieve 85% at a HR of 0.30 is virtually certain.

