### **3.2.2 Regulatory Review of Primary Outcome Compliance**

CPP has received advice from both the FDA and the EMA concerning the test method and criteria (Sections 3.2 and 5.) to be used when analyzing the primary study outcome, including the value of alpha.

The US Food and Drug Administration (FDA) noted that the comparison of single agent CPP-1X vs. combination treatment will not provide information about the treatment effect of CPP-1X (i.e. eflornithine), and therefore this result will not be included in the product label. Therefore, the primary analysis of import to FDA is the comparison of single agent sulindac vs. combination treatment.

The European Medicines Agency (EMA) noted that for the three arm trial design the superiority of the combination treatment must be tested against both mono-components. The combination treatment must be shown to be superior to both mono-components, or else the results will be considered inconclusive. As a consequence, consistent with EMA/SAWP commentary, alpha does not need to be adjusted for multiplicity and two separate 5% two-sided tests will suffice.

To harmonize the advice provided by these two Agencies, CPP will sequentially perform the two primary comparisons as part of the primary analysis, each at the 2-sided  $p = 0.05$  level. All information concerning these comparisons will be clearly provided to both Agencies. The single treatment comparison requested by FDA will be available, as will the two comparisons requested by EMA, both at the requested level of alpha. This approach fulfills the differing requirements for the primary comparison as asked for by each Agency.

We note that this approach is both a fixed-sequence and gatekeeping approach. It is fixed-sequence in that the comparison of combination with single-agent Sulindac takes place before the comparison of combination with single-agent Eflornithine and the first serves as a gatekeeper for the second (i.e., no declaration of significance in the second comparison will be made if the first comparison is not significant at the 0.05 level). Therefore, the type I error in the sequential testing is well controlled. In addition, because *both* tests must be significant for EMA approval, the type I error of the second test in the sequence is less than 0.05.

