### 5.3 Hazard Rates

Because the power of time-to-event analyses depends on the total number of observed primary endpoints (“events”) and the hazard ratio in a given two-arm comparison of a single-agent versus combination therapy, we translate the above doubling of two-year event-free proportions into hazard ratios under a simplifying assumption of exponentially distributed time-to-event. Note that the primary analysis described below, in Section 7.3, does not rely on such an assumption and provides a statistically valid test of the null hypothesis even if hazard rates are not constant. Furthermore, the stratified log-rank test is an optimal test (locally most powerful) under the assumption that the *ratio* of the two groups’ hazard functions remains constant over time (the proportional hazards assumption). Note that the much stronger assumption, that the individual hazard functions themselves remain constant over time, would be dubious in this trial.

Therefore, irrespective of how the two-year event-free proportions are translated into hazard ratios, it is the latter which forms the *design alternative parameter* for the trial.

Under the exponential assumption, the hazard ratio (HR) comparing one treatment arm to another is given by the natural logarithm of the two-year event-free proportion for the first arm divided by the natural logarithm of the two-year event-free proportion for the other arm. Thus if the combination arm is assumed to have a two-year event-free proportion of 60%, which is double that of the 30% two-year event-free proportions assumed for the single-agent arms, the HR is  $\{\log(0.60) / \log(0.30)\} = 0.4243$ . *This is the design alternative hazard ratio for this trial* as it represents the minimum clinically meaningful treatment effect desired for the combination therapy compared to either single-agent therapy. Insofar as the combination therapy may have a two-year event-free proportion of *at least* 60%, and may prove to be perhaps 70% or greater, the design alternative HR of 0.4243 is conservative; the true (albeit unknown) HR is thought possibly to range from 0.4243 down to  $0.30 = \{\log(0.70) / \log(0.30)\}$  (see discussion below).

Given that the primary hypotheses are stated in terms of comparing either single-agent arm to the combination arm, we note that the equivalent design alternative hazard ratio becomes  $\{\log(0.30) / \log(0.60)\} = 1/0.4243 = 2.357$ .

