For the anticipated range of hazard ratios, 25 to 49 events would be needed for each two-group comparison at the 2-sided 0.05 level to achieve 85% power [3, 4]. Assuming two-year event proportions of 70% in either of the two single-agent groups and 30% to 40% in the combination arm with 50 patients per arm, the expected number of patients with an FAP-related event in either of the two single-agent groups would be 35 and 15 - 20 in the combination arm. The study design expectation is to have 50 - 55 patients with a FAP-related event in each two arm comparison, achieving at least 85% power under the design alternative. The standard deviation around the expectation of 55 events is 4.74, so observing the required number of 49 events or more would be highly likely (the probability is about 91%). If the total number of events in either comparison were only 43, there will still be 80% power to declare a significant treatment

difference under the design alternative of 0.4243.

As the two-year event proportion in the combination arm decreases from 40% with a corresponding decrease in the hazard ratio, the likelihood of observing the required number of events to maintain 85% power actually increases. For example, at the lower expectation of 50 events arising from an assumed two-year event proportion of 30% in the combination arm, the standard deviation of the total number of events in a two-arm comparison decreases to 4.58 and the probability that the observed number of events will exceed the 25 required to achieve 85% at a HR of 0.30 is virtually certain.

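### The stated power of at least 85% for either comparison is single-test power; under the plan's own gate the final analysis delivers it only for the sulindac comparison

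*SAP*

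**What the plan says.** **Power.** SAP 5.2 item 3 and Protocol 12.4.1 item 3 set the target: "Power of at least 85% to detect the above-mentioned treatment effect comparing either of the two single treatment arms to the combination arm". Protocol 12.4.2 and SAP 5.3 expect 50 to 55 events "in each two arm comparison, achieving at least 85% power under the design alternative". They give 49 events as the requirement at the design hazard ratio and 25 at the optimistic end of the range. For a lower count, SAP 5.3 says "If the total number of events in either comparison were only 43, there will still be 80% power"; Protocol 12.4.2 has the same sentence and words the result as "there will still be 80% power to declare a significant treatment difference under the design alternative of 0.4243". SAP Table 5.1 adds power of 0.8705 at 52 events and 0.8881 at 55, for either two-arm comparison.

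**Effect size.** The design hazard ratio is 0.4243, of which SAP 5.3 says "it represents the minimum clinically meaningful treatment effect desired for the combination therapy compared to either single-agent therapy".

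**Decision rule.** The two comparisons are tested in a fixed order, sulindac then CPP-1X. Protocol 12.1 says "the first serves as a gatekeeper for the second", and SAP 3.2.2 spells out that "no declaration of significance in the second comparison will be made if the first comparison is not significant at the 0.05 level". SAP 3.2.2 reports the EMA position as "The combination treatment must be shown to be superior to both mono-components, or else the results will be considered inconclusive".

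**The concern.** The power sections treat the two comparisons alike, but the decision rule does not. The sulindac test can be declared on its own. At the final analysis the CPP-1X test can be declared only if both tests are significant, and the probability of that is lower than the power of either test alone. Neither document reports it.

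The plan does use the both-must-win condition elsewhere. SAP 3.2.2 and Protocol 12.1 rely on it to argue that the type I error of the second test is below 0.05. The same condition lowers the power of that test, and the power sections do not carry this over.

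At stake is how the trial's chance of success is read at the smallest effect the plan calls clinically meaningful. For the CPP-1X comparison, the stated figures imply a risk of missing a true effect of about 15% at 49 events and 11% at 55. Under the gate the risk is about 24% and 19%.

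**Working it through.** **Inputs from the documents**
- Two-year event-free proportions of 0.30 (each single agent) and 0.60 (combination): SAP 3.1 and 5.3.
- Equal event rates in the two single-agent arms: SAP 5.2 item 4. Both comparisons then have the same hazard ratio (HR).
- Final critical value 1.962: SAP 5.4.2 and 7.4.
- 1:1:1 allocation (SAP 6), with the combination arm common to both tests (SAP 3.2).
- Information equal to events divided by 4: SAP 7.4.

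**Input not in the documents.** The correlation between the two Z-scores. I assume 0.5, which follows from equal allocation with a shared arm, and show 0.3 to 0.7.

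**Step 1: reproduce the plan's figures.**
- HR = log(0.60)/log(0.30) = 0.4243, so θ = −log(0.4243) = 0.857.
- Schoenfeld events for 85% power at two-sided 0.05: 4 × (1.960 + 1.036)² / θ² = 48.9, so 49. At HR = log(0.70)/log(0.30) = 0.296 the result is 24.3, so 25. Both match.
- Single-test power with D events is Φ(θ√(D/4) − 1.962). For D = 49: 0.857 × 3.5 = 3.001, and Φ(3.001 − 1.962) = Φ(1.039) = 0.851. For D = 43, 52 and 55 it is 0.802, 0.871 and 0.888.
- Integrating over the interim boundaries gives 0.8704 at 52 events and 0.8881 at 55. These agree with Table 5.1 to within 0.0001.

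**Step 2: apply the gate.** Both-win power is P(Z₁ ≥ 1.962 and Z₂ ≥ 1.962), where the Z-scores are bivariate normal, each with mean θ√(D/4).

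| Events per comparison | Single test | Both win, correlation 0.5 | Range, correlation 0.3–0.7 |
|---|---|---|---|
| 43 | 0.80 | 0.69 | 0.67–0.72 |
| 49 | 0.85 | 0.76 | 0.74–0.78 |
| 52 | 0.87 | 0.79 | 0.77–0.81 |
| 55 | 0.89 | 0.81 | 0.80–0.83 |

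Both-win power of 0.85 at the design HR needs 59.7 events per comparison (61.0 at correlation 0.3, 57.7 at 0.7).

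**Step 3: dependence on the hazard ratio.** At correlation 0.5, both-win power reaches 0.85 at HR 0.388 with 49 events and at about 0.41 with 55. Single-test power at those points is 0.91. At HR 0.296, both-win power is 0.98 with 50 events but 0.77 with the 25 events the plan lists for that HR.

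**Step 4: interim look.** SAP 5.4.2 and Protocol 12.8 state the 3.2905 boundary for either comparison and mention no gate. Counting an ungated interim crossing for CPP-1X raises its power from 0.758 to 0.764 at 49 events and from 0.814 to 0.819 at 55. The EMA criterion is unaffected.

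**Step 5: simulation check.** Three-arm trials with exponential hazards, no dropout and an unstratified log-rank test, 60,000 replicates per setting:
- 50 per arm followed for 24 months (55.0 events per comparison): single-test 0.883, both-win 0.807.
- 57 per arm stopped at 90 events in total, simultaneous entry (54.6 per comparison): 0.887 and 0.813.
- The same with entry spread over 21 months, an assumption based on the randomization dates (54.8 per comparison): 0.876 and 0.797.

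The simulated correlation was 0.495 to 0.500.

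**The case against.** The strongest reply is that the power text is framed per comparison throughout, that every figure is arithmetically right for one test, and that a reader can see the gate. This stands for the sulindac comparison, which SAP 3.2.2 identifies as the one that matters to FDA. It does not stand for CPP-1X: the text applies power to declare significance to either comparison, and the gate withholds that declaration whenever the sulindac test fails.

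A second reply is that 0.4243 is described as conservative, with a true HR possibly near 0.30. This limits the reach of the point. With 49 to 55 events, both-win power meets 85% once the HR is about 0.39 to 0.41 or lower. But 0.4243 is also the plan's minimum meaningful effect, and the 85% target is set there.

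A third is that 171 patients were randomized instead of 150. The trial stops at 90 events in total, however, which at the design split of 35/35/20 is 55 per comparison. Protocol 3.2 reports 53 events by June 2017 and doubts that 90 will be reached.

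Three stronger readings are tempting and are not supported:
- *The plan claims 85% power for the EMA criterion.* It gives no figure for that criterion.
- *The 85% in Protocol 3.2 is per comparison, so its both-win counterpart is 0.76.* That section refers to Weibull analyses that are not shown. It does not say whether the power is per comparison or joint, or which hazard ratio applies.
- *The difference between stated and gated power vanishes at HR 0.39 to 0.41.* Only the shortfall against 85% does; both-win power there is 0.85 against 0.91 for a single test.

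**Conclusion.** The point holds as a mismatch between the stated power and the decision rule. At the design HR, power to declare the CPP-1X comparison at the final analysis, which equals the power to meet the EMA criterion, is about 9 percentage points below the single-test figure at 49 events (0.76 against 0.85). It is about 7 points below at 55 (0.81 against 0.89) and 11 below at 43 (0.69 against 0.80). The sulindac figure is right as it stands.

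The result rests on the plan's own HR, equal single-agent event rates, the normal approximation and the assumed correlation. The correlation matters little: over 0.3 to 0.7 every value at 43 to 55 events stays below 0.85. The simulation was unstratified, whereas the planned test is stratified.

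This does not show a type I error problem, a wrong event calculation for a single test, or a need for more patients. What is missing is a power figure for the gated test and for winning both.

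**What to change.** In Protocol 12.4, SAP 5.2 item 3, SAP 5.3 and SAP Table 5.1, label the existing figures as single-test (marginal) power, delivered in full only for the sulindac comparison. Add one line along these lines: at HR 0.4243, power at the final analysis for the gated CPP-1X comparison, equal to the power to win both comparisons, is 0.69, 0.76, 0.79 and 0.81 at 43, 49, 52 and 55 events per comparison (correlation 0.5 assumed; ranges 0.67–0.72, 0.74–0.78, 0.77–0.81 and 0.80–0.83 for correlations 0.3 to 0.7).

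For Protocol 3.2, at most ask the sponsor whether the Weibull-based 85% is per comparison or for winning both, and under which hazard assumptions.

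These are text and table edits. Tests, alpha, boundaries, event target and patient numbers do not change. The only cost is a less favourable stated power for CPP-1X and the EMA criterion.

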### 5.3 Hazard Rates

Because the power of time-to-event analyses depends on the total number of observed primary endpoints (“events”) and the hazard ratio in a given two-arm comparison of a single-agent versus combination therapy, we translate the above doubling of two-year event-free proportions into hazard ratios under a simplifying assumption of exponentially distributed time-to-event. Note that the primary analysis described below, in Section 7.3, does not rely on such an assumption and provides a statistically valid test of the null hypothesis even if hazard rates are not constant. Furthermore, the stratified log-rank test is an optimal test (locally most powerful) under the assumption that the *ratio* of the two groups’ hazard functions remains constant over time (the proportional hazards assumption). Note that the much stronger assumption, that the individual hazard functions themselves remain constant over time, would be dubious in this trial.

Therefore, irrespective of how the two-year event-free proportions are translated into hazard ratios, it is the latter which forms the *design alternative parameter* for the trial.

Under the exponential assumption, the hazard ratio (HR) comparing one treatment arm to another is given by the natural logarithm of the two-year event-free proportion for the first arm divided by the natural logarithm of the two-year event-free proportion for the other arm. Thus if the combination arm is assumed to have a two-year event-free proportion of 60%, which is double that of the 30% two-year event-free proportions assumed for the single-agent arms, the HR is  $\{\log(0.60) / \log(0.30)\} = 0.4243$ . *This is the design alternative hazard ratio for this trial* as it represents the minimum clinically meaningful treatment effect desired for the combination therapy compared to either single-agent therapy. Insofar as the combination therapy may have a two-year event-free proportion of *at least* 60%, and may prove to be perhaps 70% or greater, the design alternative HR of 0.4243 is conservative; the true (albeit unknown) HR is thought possibly to range from 0.4243 down to  $0.30 = \{\log(0.70) / \log(0.30)\}$  (see discussion below).

Given that the primary hypotheses are stated in terms of comparing either single-agent arm to the combination arm, we note that the equivalent design alternative hazard ratio becomes  $\{\log(0.30) / \log(0.60)\} = 1/0.4243 = 2.357$ .

For the anticipated range of hazard ratios, 25 to 49 events would be needed for each two-group comparison at the 2-sided 0.05 level to achieve 85% power [3, 4]. Assuming two-year event proportions of 70% in either of the two single-agent groups and 30% to 40% in the combination arm with 50 patients per arm, the expected number of patients with an FAP-related event in either of the two single-agent groups would be 35 and 15 - 20 in the combination arm. The study design expectation is to have 50 - 55 patients with a FAP-related event in each two arm comparison, achieving at least 85% power under the design alternative. The standard deviation around the expectation of 55 events is 4.74, so observing the required number of 49 events or more would be highly likely (the probability is about 91%). If the total number of events in either comparison were only 43, there will still be 80% power to declare a significant treatment

difference under the design alternative of 0.4243.

As the two-year event proportion in the combination arm decreases from 40% with a corresponding decrease in the hazard ratio, the likelihood of observing the required number of events to maintain 85% power actually increases. For example, at the lower expectation of 50 events arising from an assumed two-year event proportion of 30% in the combination arm, the standard deviation of the total number of events in a two-arm comparison decreases to 4.58 and the probability that the observed number of events will exceed the 25 required to achieve 85% at a HR of 0.30 is virtually certain.

